
research purposes; the only visits will be part of the standard of care. Surgical residents will maintain a list of study patients on whom they are called to evaluate for postoperative bleeding in the recovery unit. They will be blinded to whether the patient received the study medication or placebo. Records (i.e. via STARR) will be queried to determine the frequency with which patients in each group call the clinic or answering service with bleeding- related concerns. Records of further intervention (nasal packing, cautery, return to OR) will also be gathered. These outcomes will be used to determine the difference between groups. Patients will have received the standard of care for postoperative epistaxis in all these scenarios, identical to patients who are not enrolled in the study. The primary outcome is the patient-reported VAS bleeding score after surgery. This methodology has been used by other published work to assess the impact of agents used at the end of procedures to reduce the rate of postoperative bleeding after sinonal surgery (<https://journals.sagepub.com/doi/10.1016/j.otohns.2009.06.078>). Using their results as a reference, we may expect that the VAS score on postoperative day one may drop from a 4 to a 2. Assuming an SD of 1.6-1.8 for the purpose of estimations, we would need 24-28 total cases to detect the effect size of 2 in VAS if using 1:1 ratio with 80% power. The secondary outcome is the frequency with which the service is requested to evaluate patients in the recovery unit for postoperative bleeding concerns after sinonal surgeries. Anecdotal feedback from the resident service suggests that they are requested to evaluate roughly 30% of these patients. With the hypothesis that the TXA could reduce the frequency by roughly half to 15%, we will require 118 patients in each group (total N=236) to achieve 80% power to detect a difference between the two group proportions of 15% (with 30% in placebo, 15% in TXA group). This estimate uses two sided Z-test while assuming type I error=0.05.

b. Procedure Risks

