7. DISINFECTION PROCEDURES FOR MEDICAL EQUIPMENT USED ON BOTH HUMANS AND ANIMALS

N/A

8. PARTICIPANT POPULATION**a. Planned Enrollment**

All patients will be recruited at Stanford Sinus Center. Given the expected number of patients to power the study based on the calculations listed in section 2a, this will include approximately 250 total patients. To be included, patients will have to be scheduled for sinonasal surgery, as this is the population of interest. While students and employees will not be specifically targeted, they also will not be specifically excluded. Patients with surgery for sinonasal cancer will be excluded as this study will focus on routine sinonasal surgery for nasal obstruction and/or chronic rhinosinusitis.

b. Age, Gender, and Ethnic Background

Patients will include both men and women 18 years of age or older from all ethnicities that present to Stanford outpatient clinics.

c. Vulnerable Populations

Children, pregnant women, homeless, and decisional impaired patients will be excluded from the study. Students, employees, and economically and educationally disadvantaged patients will be offered the opportunity to participate in the study, however it will be made clear that if they choose not to participate they will otherwise still receive the identical standard of care. There will be no pressure to participate given the high volume of patients that are scheduled for surgery through the sinus center.

d. Rationale for Exclusion of Certain Populations

This study will only be implemented at the adult hospital. Children do not receive surgical care at the adult hospital, but rather only at LPCH. As such, by necessity, they will be excluded.

e. Stanford Populations

Laboratory personnel, employees, and students are eligible for the study, but will not be specifically targeted. All those who have been scheduled for sinonasal surgery who do not meet the exclusion criteria (pregnant women, children, prisoners, international, etc) will be offered participation in the study. No participants will receive compensation.

f. Healthy Volunteers

N/A - all patients will have a diagnosis code requiring sinus or nasal surgery

g. Recruitment Details

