Once enrollment begins, the expected duration of the study is expected to be 6-12 months depending on speed of enrollment. Screening will take roughly 10 minutes during the preoperative clinic visit. Active participation in the study will last from the day of surgery to the first scheduled clinical visit one week later. Analysis of patient data will be performed quarterly.

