The intervention medication will be administered in the operating room under the supervision of the anesthesia team. Any unexpected side effects will be identified and addressed at that time. As a matter of routine, patients are watched in the recovery unit after surgery for a period of approximately two hours. The half-life of the IV formulation of tranexamic acid is 2 hours, and so any side-effects should be noted prior to discharge home.

To reduce the risk of data breach, data will be coded after the completion of the patient's participation, which will terminate at the first clinical follow-up visit one week after surgery, at which time they will submit their bleeding journal template. Data will be stored only on a encrypted laptop, and if sharing is required will be done through Stanford-sponsored secure data sharing platforms such as Box.

d. Study Conclusion

As above, active individual patient participation terminates at one week postoperatively. All the data necessary for analysis will have been gathered at this time. This data will still be analyzed along with the remainder of the patients until the time of study completion, which is expected to be 6-9 months later once an adequate number of patients have been recruited.

As above, patients will continue to receive the routine standard of care during this study. Epistaxis is expected after sinonasal surgery and is addressed in a variety of ways (observation, holding pressure, nasal sprays, nasal packing, return to OR). The purpose of this study is to determine whether this inherent risk of bleeding can be reduced. All of these interventions are still available and will be used as clinically indicated.

e. Data Safety Monitoring Plan (DSMC)

i. Data and/or events subject to review

Data that will be collected include study-related adverse events (e.g. thrombosis, nausea requiring overnight admission) and any serious adverse events (e.g. death), suspected serious adverse reactions, and unanticipated problems. Outcomes data will be analyzed every 3 months to assess progress toward study endpoints and to ensure no unanticipated risks of study participation.

ii. Person(s) responsible for Data and Safety Monitoring

[name] (PD)

iii. Frequency of DSMB meetings

Meetings will occur quarterly. If deemed necessary by the IRB, written recommendations will be submitted after each meeting, to include plans to continue the study as designed, continue with modification, temporarily suspend, or terminate.

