iv. Specific triggers or stopping rules

The study will end when recruitment targets are reached or if interim data analysis demonstrates a statistically significant difference in endpoints between groups. If Suspected Unexpected Serious Adverse Reactions or Unanticipated Problems (UPs) are encountered, the study will be halted and possibly terminated early if the issue cannot be resolved.

v. DSMB Reporting

The outcome of the review will be disseminated to the co-investigators and the IRB.

vi. Will the Protocol Director be the only monitoring entity? (Y/N)

Yes

vii. Will a board, committee, or safety monitor be responsible for study monitoring? (Y/N)

No

f. Risks to Special Populations

N/A

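### The efficacy stopping rule in section 9.e.iv has no significance level, boundary or named endpoint; testing one endpoint at 0.05 at each quarterly look would raise the false-positive rate from 5% to about 8-14%.

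*Combined protocol and SAP*

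**What the plan says.** Section 9.e.iv gives two routes by which the trial ends, besides a separate safety halt: "The study will end when recruitment targets are reached or if interim data analysis demonstrates a statistically significant difference in endpoints between groups".

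The looks are scheduled. Section 9.e.i says "Outcomes data will be analyzed every 3 months to assess progress toward study endpoints", and section 8.m says "Analysis of patient data will be performed quarterly". On length, 8.m says "the expected duration of the study is expected to be 6-12 months depending on speed of enrollment", while 9.d refers to "study completion, which is expected to be 6-9 months later once an adequate number of patients have been recruited".

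The only significance level in the document is the two-sided 0.05 in section 2.a, used in the fixed-sample calculation for the recovery-unit outcome (30% vs 15%, 236 patients). The VAS calculation in 2.a needs 24-28 patients and is set on day one: "we may expect that the VAS score on postoperative day one may drop from a 4 to a 2". Section 2.g instead defines the primary endpoint as VAS and gauze use over the first week, and lists three secondary endpoints. Section 8.a sets enrolment: "this will include approximately 250 total patients".

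Section 2.g also describes what may follow a significant interim difference: a possible discussion with the IRB, with standard of care expected to continue until the study ends. Section 9.e.vi asks "Will the Protocol Director be the only monitoring entity" and answers yes; 9.e.vii confirms that there is no board or committee.

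**The concern.** Each unadjusted look gives chance another opportunity to produce a significant result, and this rule turns such a result into the end of the trial. Under no effect, about half of the false stops would favour TXA. The study's stated purpose is to give surgeons a rationale for routine use, so a false positive in that direction matters.

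The rule also does not say which endpoint counts. It could mean any one of those listed in 2.g or several jointly, and these readings have very different error rates. With no independent monitoring body, the level and the endpoint could be chosen by people who have already seen the data.

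Finally, the rule conflicts with the two sample sizes. VAS was planned to be detectable with about a tenth of the patients that the recovery-unit outcome needs (28/236 = 12%). A stop on VAS could therefore end the trial well before the outcome that sets the enrolment target can be assessed.

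**Working it through.** **The plan's own figures reproduce.**
- Recovery-unit outcome, unpooled two-sided Z-test: n = (0.30×0.70 + 0.15×0.85)(1.960 + 0.842)² / 0.15² = 117.7, so 118 per group and 236 in total.
- VAS, two-sample t-test, difference 2: 11.1 per group at SD 1.6 and 13.7 at SD 1.8, so 24 and 28 in total.

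**Number of looks.** Quarterly looks over 6-12 months (8.m) give 6/3 = 2 to 12/3 = 4. Section 9.d's 6-9 months, if read as study length, gives 2 to 3. These counts treat the last quarterly look as the final analysis. If the final analysis is separate, there are 3-5 looks.

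**False-positive rate, one endpoint.** Assume |Z| > 1.96 at every look. With Z_k the statistic at information fraction t_k, corr(Z_j, Z_k) = √(t_j/t_k) for j < k. The overall rate is 1 − P(|Z_k| ≤ 1.96 for all k), computed by recursive numerical integration with equal spacing:

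| Looks | Overall two-sided error |
|---|---|
| 1 | 5.0% |
| 2 | 8.3% |
| 3 | 10.7% |
| 4 | 12.6% |
| 5 | 14.2% |

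Uneven spacing changes this modestly:
- Two looks: 9.4% with the first at 12.7% of the data, 7.3% with the first at 75%.
- Slow start, looks at 0.13/0.37/0.68/1: 13.9%.

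**Two endpoints, VAS and gauze use** (1,000,000 simulated trials, correlation 0.3-0.7 assumed):

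| Looks | Either can trigger | Both needed at the same look |
|---|---|---|
| 2 | 13.5-15.5% | 0.9-2.9% |
| 3 | 17.4-19.8% | 1.2-3.9% |
| 4 | 20.3-23.1% | 1.5-4.6% |

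**Chance of stopping on VAS at the first look, and what is left for the recovery-unit outcome.** VAS: two-sample t-test at 0.05, SD 1.8 to 1.6. Recovery unit: pooled Z-test, 30% vs 15%. The first-look sizes and the halved VAS difference are assumptions; the document gives no effect or SD for VAS over the first week.

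| Patients at first look | VAS, difference 2 | VAS, difference 1 | Recovery-unit power |
|---|---|---|---|
| 30 | 84-91% | 31-38% | 16% |
| 40 | 93-97% | 40-49% | 20% |
| 59 | 98.7-99.7% | 55-66% | 28% |

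At a quarter to a half of 236-250 patients (59 to 125), recovery-unit power is 28-52%. At 236 the same test gives 79%, in line with the planned 80%.

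**The case against.** The strongest objection is that every error rate here is conditional. The plan never says that 0.05 applies at the interim looks, so the demonstrated fault is an undefined rule, and the inflation follows only on one reading. If both primary measures had to be significant together, the rate would be below 5%. This is fair, and it is why the figures are stated as conditional. It does not rescue the rule: 0.05 is the only level in the document, and nothing states the joint reading.

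A second objection concerns the upper end. Five equally spaced looks do not fit a 12-month calendar, because follow-up lasts one week and a separate final analysis would come just after the last quarterly look. With even accrual, looks at 0.23/0.48/0.73/0.98/1 give 13.2%, and for a 6-month study looks at 0.46/0.96/1 give 9.2%. This is correct for even accrual. A slow start with a separate final analysis (0.13/0.37/0.68/0.98/1) gives 14.3%, so 8-14% remains a reasonable summary.

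Third, even accrual of 250 patients over 6-12 months would put about 62-125 patients at the first look, so 30 or 40 implies a slow start. That stands. The 28-52% power range for a first look at a quarter to a half of 236-250 patients covers the even-accrual case.

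Fourth, if the planning values are true, a stop on VAS is a correct finding on the primary outcome. That also stands; the loss is then in the secondary outcome, which nevertheless sets the trial's size.

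Fifth, 2.g may mean only that clinical practice stays unchanged until the study ends, and 9.d may not be a second statement of study length. Both readings are possible. The 2.g text is therefore better treated as unreconciled with 9.e.iv than as a plain contradiction.

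**Conclusion.** The concern holds and should be fixed before any between-group look at outcomes. Section 9.e.iv is an operative stopping rule tied to scheduled analyses, and it lacks everything needed to control type I error. At two-sided 0.05 per look on one endpoint, the overall error is 8.3-12.6% for 2-4 equally spaced looks and 14.2% for 5, instead of 5%. By symmetry about half of that, roughly 4-7%, would be false stops or final results in favour of TXA. If either primary measure can trigger, the rate is about 14-23% for 2-4 looks at the assumed correlations.

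The early-stop result rests on VAS being allowed to trigger and on the day-one planning values holding. With half the planned difference, the chance of a first-look stop falls to 31-66% across the assumed sizes, which is still substantial.

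**What to change.** **Preferred change.** In 9.e.iv, delete the second condition, so that no interim efficacy result ends the study, and leave the separate safety halt unchanged. In 8.m and 9.e.i, limit the quarterly reviews to safety, recruitment and data quality, with no between-group efficacy test before the final analysis.

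**If an efficacy stop is wanted.** Name one endpoint and one time point, state the number of looks, and use an O'Brien-Fleming-type spending function with total two-sided alpha 0.05. For equally spaced looks the critical |Z| values are:
- 2 looks: 2.96, 1.97
- 3 looks: 3.71, 2.51, 1.99
- 4 looks: 4.33, 2.96, 2.36, 2.01

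Recompute them from the spending function at the information actually available; used unchanged at 0.13/0.37/0.68/1, the four-look values give 5.2%. If the endpoint is VAS, say whether it is day one (2.a) or the first week (2.g). State also that crossing the boundary settles the VAS comparison only, and that enrolment continues to 236 for the recovery-unit outcome.

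In either case, reconcile 2.g with 9.e.iv on what follows a significant interim result.

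**Cost.** Deleting the clause is a wording change and needs no patients; it gives up an unrestricted early stop for benefit. The spending boundary on the 30% vs 15% comparison raises the maximum N from 236 to 238 (2 looks), 240 (3) or 242 (4 or 5), all within the planned 250.

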10. BENEFITS

Participants in the study may receive direct benefit if the administration of tranexamic acid does indeed reduce postoperative bleeding, and assuming the participant receives tranexamic acid rather than placebo. Because this is not yet proven, and this study is designed to evaluate this, this is a potential benefit and not a certain benefit. Furthermore, if the patient receives placebo, they will receive no benefit, and will have received the routine standard of care.

If the data gathered from the study is able to show a benefit without additional risks with the administration of a dose of tranexamic acid, then future patients may benefit from this knowledge with a change in the routine standard of care. Given that this type of surgery is one of the most common in the United States, many future patients may have a more favorable postoperative course if the volume of bleeding is able to be reduced effectively.

11. PRIVACY AND CONFIDENTIALITY

All participant information and specimens are handled in compliance with the Health Insurance Portability and Accountability Act (HIPAA) and privacy policies of Stanford University, Stanford Health Care, and Stanford Children's Health.
